## 2. TABULAR PRESENTATION OF TIMING OF OUTCOME MEASUREMENTS

---

Registry	Observation period	Variables relevant for this study
The Danish Knee Arthroplasty Register	January 1 st 1998 – 31 st December 2021	ID-key (number) Date of surgery (date) Code for implant type (number) Revision performed (yes/no) Revision of tibial component (yes/no) Revision of femoral component (yes/no) Laterality (left/right) Sex (male/female) Age (number) Indication for primary procedure (number) Performing institution (number) Duration of procedure (minutes)
Landspatientregisteret	January 1 st 1998 – 31 st December 2021	ID-key (number) Date of surgery (date) Code for procedure (number) Laterality (left/right) Sex (male/female) Age (number) Performing institution (number) Year of death or emigration (date)

---

### 3. ELABORATIONS ON OUTCOMES AND DATA

---

#### **Data management, The Danish Knee Arthroplasty Register:**

ID-key: unique identification key specifying patient. This key is an anonymized ID key in encrypted integer format, and hence, is **not** equal to the CPR number of the participants.

Date of surgery: The date that the procedure took place. In character (date) format.

#### Code for implant type

For the Danish knee arthroplasty register a set of codes are used to specify the inserted implant.

Primary procedures are defined as the following codes:

- 1 = TKA
- 2 = medial UKA
- 3= lateral UKA
- 4 = patellofemoral UKA
- 5+7 = rotating hinge-prosthesis
- 6 = Resection prosthesis
- 9 = Partial resurfacing
- 100 = Rotating hinge-prosthesis with condyle resection
- 104 = Resection or segmental prosthesis
- 105 = Hemicap
- 107 = Episealer
- 119 = tibiaprosthesis w. stem

#### Revision procedure performed:

If the procedure is a revision it is marked with yes, otherwise it is marked with no.

#### Definition of major revision:

A revision in DKR is defined as a major revision, if either the femoral or the tibial component has been revised. A procedure is marked as a major revision if either one of the variables "Revision of tibial component" and/or "revision of femoral component" are marked as yes.

#### Definition of major and minor revision

Major and minor revisions are defined as the following implant types:

- 1 = TKA
- 2 = medial UKA
- 3= lateral UKA
- 4 = patellofemoral UKA
- 5+7 = rotating hinge-prosthesis
- 6 = Resection prosthesis
- 9 = Partial resurfacing
- 10 = articulated cement spacer
- 11 = fixated cement spacer
- 100 = Rotating hinge-prosthesis with condyle resection
- 103 = Removal of patella component
- 104 = Resection or segmental prosthesis
- 105 = Hemicap
- 107 = Episealer
- 108 = Other removal
- 109 = New liner
- 110 = New patella component
- 112 = Exchange of femoral component

- 117 = Removal of tibia component
- 119 = Insertion of stemmed tibia component
- 120 = Exchange of tibia component

Laterality: Code for specifying right/left knee. 1 = right, 2 = left

Sex: Specifying the sex of the patient. M = male, F = female

Age: Number specifying the age of the patient at the time of performed procedure

Indication for primary procedure: Code specifying the indication for performing the primary procedure. The codes are:

- 1 = Idiopathic knee osteoarthritis
- 2 = Secondary arthritis
- 3 = Sequelae after tibia condyle fracture
- 4 = Sequelae after femur condyle fracture
- 5 = sequelae after patella fracture
- 6 = Rheumatoid arthritis
- 7 = Sequelae after other arthritis
- 8 = Haemophilia
- 9 = Tumour - primary
- 10 = Tumour – metastasis

Performing institution: Code specifying the performing institution. The codes are classified as SHAK-codes, developed by "Sundhedsdatastyrelsen". (<https://medinfo.dk/sks/brows.php>)

Duration of procedure: Number specifying the duration of the performed procedure. Given as minutes.

**Data management, Landspatientregisteret:**

ID-key: unique identification key specifying patient. This key is an anonymized ID key in character format, and hence, is **not** equal to the CPR-number of the participants.

Date of surgery: The date that the procedure took place. In character (date) format.

Code for procedure: NOMESCO procedure codes are used in Landspatientregisteret. KNGB\* codes specify primary procedures, whereas KNGC\* codes specify revision procedures.

Definition of major revisions in Landspatientregisteret

Revision procedures are marked with KNGC\* codes. The following KNGC codes define a major revision:

- KNGC01: Secondary insertion of proximal component of uncemented partial prosthesis in knee
- KNGC02: Secondary insertion of distal component of uncemented partial prosthesis in knee
- KNGC03: Secondary insertion of patellofemoral component of uncemented partial prosthesis in knee
- KNGC04: Secondary insertion of multiple components of uncemented partial prosthesis in knee
- KNGC11: Secondary insertion of proximal component of cemented partial prosthesis in knee
- KNGC12: Secondary insertion of distal component of cemented partial prosthesis in knee
- KNGC13: Secondary insertion of patellofemoral component of cemented partial prosthesis in knee
- KNGC14: Secondary insertion of multiple components of cemented prosthesis in knee
- KNGC19: Secondary insertion of cemented partial prosthesis in knee without specification
- KNGC20: Secondary insertion of all components in uncemented total prosthesis in knee
- KNGC21: Secondary insertion of proximal component in uncemented total prosthesis in knee
- KNGC22: Secondary insertion of distal component in uncemented total prosthesis in knee
- KNGC24: Secondary insertion of multiple components un uncemented total prosthesis in knee
- KNGC29: Secondary insertion of uncemented total prosthesis in knee without specification

KNGC30: Secondary insertion of all components of hybrid total prosthesis in knee  
KNGC31: Secondary insertion of proximal component of hybrid total prosthesis in knee  
KNGC32: Secondary insertion of distal component of hybrid total prosthesis in knee  
KNGC34: Secondary insertion of more than one component of hybrid total prosthesis in knee  
KNGC39: Secondary insertion of hybrid total prosthesis in knee without specification  
KNGC40: Secondary insertion of all components of cemented total prosthesis in knee  
KNGC41: Secondary insertion of proximal component of cemented total prosthesis in knee  
KNGC42: Secondary insertion of distal component of cemented total prosthesis in knee  
KNGC44: Secondary insertion of multiple components of cemented total prosthesis in knee  
KNGC49: Secondary insertion of cemented total prosthesis in knee without specification  
KNGC99: Other secondary insertion of prosthesis in knee

#### Definition of minor revisions in Landspatientregisteret

Minor revisions are defined as the KNGC codes listed here:

KNGC02A: Secondary insertion of only polyethylene liner in uncemented partial prosthesis in knee  
KNGC09: Secondary insertion of uncemented partial prosthesis in knee without specification  
KNGC1: Secondary insertion of cemented partial prosthesis in knee  
KNGC12A: Secondary insertion of only polyethylene liner in cemented partial prosthesis in knee  
KNGC22A: Secondary insertion of only polyethylene liner in uncemented total prosthesis in knee  
KNGC23: Secondary insertion of patellofemoral component in uncemented total prosthesis in knee  
KNGC32A: Secondary insertion of only polyethylene liner in hybrid total prosthesis in knee  
KNGC33: Secondary insertion of patellofemoral component in hybrid total prosthesis in knee  
KNGC42A: Secondary insertion of only polyethylene liner in hybrid total prosthesis in knee  
KNGC43: Secondary insertion of patellofemoral component of cemented total prosthesis in knee  
KNGC59: Secondary insertion of interpolated prosthesis in knee  
KNGC59A: Insertion of spacer in knee in connection with revision  
KNGC99A: Secondary insertion of patella component  
KNGS49: Incision or revision with placement of medication in case of infection in knee joint

Laterality: Code for specifying right/left knee. TUL1 = right, TUL2 = left

Sex: Specifying the sex of the patient. M = male, F = female

Age: Number specifying the age of the patient at the time of the performed procedure

Performing institution: Code specifying the performing institution. The codes are classified as SHAK-codes, developed by "Sundhedsdatastyrelsen". (<https://medinfo.dk/sks/brows.php>)

Year of death: The year in which the patient has died. The patient will be marked as "ALIVE" if death has not occurred at the end of the observation period.

#### **Data management, for both registers.**

Definition of a revision: A revision is defined as the exchange, addition, or removal of a knee prosthesis component (1). However, knee arthrodesis and amputation are not included in this study.

Definition of major revision: A major revision is defined as exchange of the femoral component and/or the tibial component with subgroups of tibial, femoral and all component exchange (2).

Definition of minor revision: A minor revision is defined as the exchange of polyethylene liner and/or addition or revision of the patella component. Insertion/removal/exchange of spacers are also included in this category (2).

Population: The population is defined as the number of alive citizens in the state of Denmark. Annual populations are defined as the population in Denmark on the 1st of January that year. Additional data for sex and age of the population is acquired. Data for the population is acquired from Danmarks Statistik (3).

In case of disagreement between registers: In cases of discrepancy between the two registers, Landspatientregisteret will overrule the Danish Knee arthroplasty register concerning following variables:

- Laterality
- Date of surgery
- Gender
- Age
- Performing institution

In cases of discrepancy between the two registers, the Danish Knee arthroplasty register will overrule Landspatientregisteret concerning following variables:

- Procedure code
- Revision of tibia
- Revision of femur
- Indication

Calculation of standardized prevalence: Annual standardized prevalence is calculated as the number of patients living with a n-grade revision during a given year as a proportion of the population in Denmark (the 1st of January that year) (3). The prevalence is then multiplied by 100,000 for standardization. This is done for each level of revision, each year. E.g., the standardized prevalence for 1998 is calculated as:

$$\text{Standardized prevalence, 1998} = \frac{\text{Number of knees living in 1998 with a } n - \text{ grade revision}}{\text{Total population in Denmark in 1998}} * 100,000$$

The prevalence is only calculated for revisions performed between January 1st 1998 and December 31st 2021.

Calculation of standardized incidence: Annual standardized incidence is calculated as the number of new n-grade revisions performed as a proportion of the population in Denmark during a specific year. The population size of Denmark is defined as the population size at January 1st for that year (3). The incidence is then multiplied by 100,000 for standardization. This is done for each level of revision, each year. E.g., the standardized incidence for 1998 is calculated as:

$$\text{Standardized incidence, 1998} = \frac{\text{Number of new } n - \text{ grade revisions in the population in 1998}}{\text{Total population in Denmark in 1998}} * 100,000$$

Missing data: We expect to encounter some missing data. All missing data will be described.

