This study is a retrospective study using nationwide information from the Danish Knee Arthroplasty Register (DKR) and Landspatientregisteret (LPR), with an evidence level of level 3 in the evidence hierarchy. The registries are used to identify all patients with a primary knee arthroplasty and with a revision knee arthroplasty from January 1st 1998 to December 31st 2021. Information regarding surgery, patient demographics and surgical technique will be obtained for statistical analysis. Data will be stored briefly on a logged drive and then transferred to the servers of Danmarks Statistik, which are encrypted. Additionally, all data is anonymized when transferred to Danmarks Statistik.

The design was chosen as there is a limited number of revisions in Denmark, and even fewer cases of re-revisions. To produce meaningful results, it is necessary to collect as much data as possible. The study will include all patients operated in Denmark from 1998-2021, which will create the best possible basis for describing the population and calculating the incidence, prevalence, cumulative revision rates and lifetime risks.

Review

The project has been registered in the Knowledge Centre for Data Reviews in Region Hovedstaden (PACTIUS), as required.

Case number: P-2022-711

This is a registry study and there is no obligation to notify the scientific ethics committee.

Description of registers, acquisition of data and description of data

Danish Knee Arthroplasty Register

Danish Knee Arthroplasty Register (DKR) is a clinical database which has existed since January 1st 1997. Registration of all knee arthroplasty procedures has been mandatory from June 1st 2006 at all Orthopedic institutions in Denmark, including private hospitals. All primary and revision procedures are recorded including information regarding the patient, procedure, indication and equipment used. In general, the degree of completeness is high for the register, with a 97% completeness rate in 2014 (3).

Landspatientregisteret

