In the event of a discrepancy between data from DKR and DS, data from DKR will be chosen, but specific rules will be created for specific situations. In case of missing data for indication for revision (for example if a procedure is not registered in DKR), DS diagnosis codes will be used.

Data is obtained from both registers, as the degree of completeness is very high in both registers. By combining data a near-perfect data collection of the population is ensured.

Description of data from DKR

The Regions' Clinical Quality Development Program (RKKP) manages data from DKR. After receiving approval from PACTIUS, RKKP was queried for data-extraction. Data has since been acquired. Data consists of primary and revision procedures performed from January 1st 1998 to December 31st in 2021. The data includes information regarding:

CPR-number (personal identification number)

Sex

Hospital

Department

Laterality of procedure

Height

Weight

Revision (yes/no)

Indication for procedure

Operation date

Type of arthroplasty

Femur fixation (Cement, yes/no)

Tibia fixation (cement, yes/no)

Femur component

Tibial component

Patella component (yes/no)

Patella fixation (cement, yes/no)

Femur stem (yes/no)

Tibia stem (yes/no)

Operating room

Use of tourniquet (yes/no)

Use of drain

Number of previous revisions

Indication for revision

First revision date

Description of data from LPR

Danmarks Statistik contains many registers about the population in Denmark, including registers regarding place-of-residence, income, education, partner-status, as well as Landspatientregisteret, which contains all information created when a patient is admitted to a public hospital. DS also contains information regarding all treatments performed in privately owned hospitals.

An application has been submitted regarding the acquisition of data from primary and revision arthroplasties performed from January 1st 1998 to December 31st 2021. The requested variables are as follows:

Name

Social Security number

Address

Changes of residence, including information on movements, emigration, disappearance, death

Income

Diagnoses/comorbidities

Operations with operation code: KNGB*, KNGC*, KNGG* and KNFQ19

Level of education

Partner status

Employment status

Statistics

After extraction of data, pooling of data in DS, creation of the populations and tables as described in the previous section on data extraction, statistical analyzes will be carried out.

WPA1

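### The SAP counts component removal as a revision, but none of its 39 LPR codes is a removal code, so isolated removals can enter only through DKR

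*SAP*

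**What the plan says.** SAP section 3, under data management for both registers, gives one definition: "A revision is defined as the exchange, addition, or removal of a knee prosthesis component". Arthrodesis and amputation are excluded.

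The two registers implement this through separate code lists.

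- **DKR.** The list of major and minor revisions includes 103 (patella component removed), 108 (other removal) and "117 = Removal of tibia component".
- **LPR.** The SAP says that KNGC "codes specify revision procedures". The major list is introduced by "The following KNGC codes define a major revision", and every code on it is worded as a secondary insertion, including the residual code "KNGC99: Other secondary insertion of prosthesis in knee". The minor list adds further insertions, spacer insertion (KNGC59A) and medication placement for infection (KNGS49).

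The Protocol, under identification of revision procedures, names the wider KNG family as a search term for revisions in the national data. Its list of requested variables is narrower: "Operations with operation code: KNGB*, KNGC*, KNGG* and KNFQ19". On DKR, the Protocol says the register has existed since 1 January 1997, that registration "has been mandatory from June 1st 2006", and that completeness was 97% in 2014. SAP section 4 records no deviations from the Protocol.

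**The concern.** One definition is turned into two different sets of events. The Protocol combines the registers so that each fills the other's gaps, but for an isolated removal the LPR lists offer no second route. If DKR missed it, the SAP's rules cannot recover it. The rule that DKR overrules LPR on procedure code does not help, because it applies only where DKR holds a record.

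Two things are at stake. First, the primary outcome is an annual series from 1998 to 2021, and the SAP hypothesises a marked rise. Any improvement in DKR capture over that period would add apparent growth in this event type. No confidence intervals, tests or sensitivity analyses are planned that might show it. Second, grade is a running count per knee, so a missed event can lower the grade of later revisions of that knee.

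A related gap is that the cross-register definitions of major revision (exchange of the femoral and/or tibial component) and minor revision (liner, patella component, spacers) do not place removal of a femoral or tibial component without replacement. The DKR rule based on the tibial and femoral revision flags might classify the same operation as major.

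**Working it through.** The plan states no figure on this point, so there is none to reproduce. The check is a count of codes, a date calculation and an illustration on stated assumptions.

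**1. Code count (SAP section 3)**

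| List | Entries | Removal entries |
|---|---|---|
| DKR, major and minor revisions (5+7 counted once) | 21 | 3 (103, 108, 117) |
| LPR, major | 25 | 0 (all secondary insertions) |
| LPR, minor | 14 | 0 (12 secondary insertions, KNGC59A, KNGS49) |

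LPR total: 25 + 14 = 39 codes, of which 0 are removals.

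**2. Routes into the combined data**

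- Removal with a listed insertion at the same operation: DKR or LPR.
- Removal with a spacer or medication placement: DKR, or LPR through KNGC59A or KNGS49, as a minor revision.
- Isolated removal, with none of these codes: DKR only.

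**3. Share of the period before mandatory DKR reporting**

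1 January 1998 to 31 December 2021 is 8,766 days. From 1 January 1998 up to 1 June 2006 is 3,073 days. 3,073 / 8,766 = 35%, and 3,073 / 365.25 = 8.4 years.

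**4. Illustrative size**

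Let r be the share of true revisions that are isolated removals, c0 the DKR completeness before June 2006 and c1 the completeness afterwards. The documents give only 97% for 2014, which is used here as c1 throughout. Assumed, with no source in the documents: r = 2–5% and c0 = 60–90%. All other revisions are taken as fully captured in both periods.

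Captured share = 1 − r(1 − c). Apparent growth from reporting alone = [1 − r(1 − c1)] / [1 − r(1 − c0)] − 1.

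- Low end, r = 0.02, c0 = 0.90: 0.9994 / 0.9980 − 1 = 0.14%.
- High end, r = 0.05, c0 = 0.60: 0.9985 / 0.9800 − 1 = 1.89%.

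The early shortfall against perfect capture, r(1 − c0), is 0.02 × 0.10 = 0.2% to 0.05 × 0.40 = 2.0%. That is not the trend artefact, because late capture is also incomplete.

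Within isolated removals alone, the apparent rise is c1 / c0: 0.97 / 0.90 = 1.08-fold to 0.97 / 0.60 = 1.62-fold.

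**5. Effect on grade**

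Take a knee with an isolated removal followed by two further revisions. The true grades are 1, 2 and 3. If the removal is missed, the later two are recorded as 1 and 2, and the knee does not reach the SAP's threshold of three for multiply revised. The exception is a removal that is the first stage of a two-stage revision. The Protocol counts that as one revision, so missing the first stage should not change the grade. The SAP does not repeat that rule and places spacer procedures among minor revisions, so the exception depends on reconciling the two documents.

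**The case against.** The case on the other side has several good parts.

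- **Spacer and infection procedures are covered.** A removal done with a spacer or medication placement can enter from LPR. This stands. A reader might infer that every removal depends on DKR, but only isolated removals do, and the documents do not say how common those are.
- **A mandatory date is not a completeness figure.** This also stands. DKR covers the whole observation period, and the Protocol describes completeness as very high in both registers. A reader might infer that removals are captured mainly in later years. The documents do not show that, and even at an assumed 60% most early removals would be captured.
- **LPR may hold the information.** A reader might infer that LPR cannot record a removal. The documents show only that the SAP's lists do not pick one up. The Protocol names the wider KNG family, and KNGS49 is on the SAP's minor list although it lies outside the Protocol's request list, so that request may not mark the true limit of the extraction. Whether a suitable removal code exists must be checked in the code book.
- **The combined data do implement removal, through DKR.** True where DKR has the record. This makes the problem a gap in one source, but the SAP does not state that the gap exists.
- **The reach is limited.** On the cross-register definition, an isolated removal is not a major revision. The series for major revisions would then be unaffected, unless the DKR component flags are ticked for removals.

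**Conclusion.** The mismatch holds: the stated definition includes removal, one register's list implements it and the other's does not. For isolated removals the combined data rest on DKR alone, and for 35% of the period DKR reporting was not mandatory and no completeness is given.

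The consequence is conditional. If DKR capture was lower before June 2006, early counts are short, the error runs towards the hypothesised increase, and some later revisions are graded too low, two-stage revisions counted as one excepted. On the assumed inputs the artefact is about 0.1–1.9% of all revisions. It is small in the total but larger within removals themselves. Its distribution across grades cannot be worked out from the documents.

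A reader might go further and infer that the reported rise would be largely an artefact, or that every later revision of an affected knee is misgraded. Neither follows. The artefact is small on the assumed range, and the Protocol's two-stage rule is an exception. This is a minor point that is worth settling before analysis because it is cheap to do so.

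**What to change.** 1. Reconcile the Protocol's revision search terms and requested codes with the SAP's LPR lists and its definition of a revision. Add the LPR procedure codes for removal of knee prosthesis components to the extraction and to the lists, after checking the code book. The Protocol's KNG search term is the place to start.
2. Assign isolated removal of a femoral, tibial or patella component to the major or minor category, identically in both registers.
3. If the codes cannot be obtained, state that isolated removals come from DKR only, and add two sensitivity series: one excluding DKR 103, 108 and 117, and one restricted to the period from June 2006. For the second, say whether knees with a primary procedure before June 2006 are kept, since their grades would still carry any earlier miss.

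Excluding 103, 108 and 117 suits a sensitivity series better than the main analysis. It narrows the cited definition and does not fully align the registers, because removals with a spacer would still enter through DKR 10 and 11 and through KNGC59A.

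The cost is a small supplementary data request under the first route, or two extra series and a sentence of limitation under the third.
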